3.5. Prior and Concomitant Medication

Prior medications are defined as medications taken prior to the first dose of open-label olanzapine. Concomitant medications are defined as medications taken on or after the first dose of open-label olanzapine. All medications as documented by the investigator will be coded using the World Health Organization Anatomical Therapeutic Chemical (WHO-ATC) drug dictionary Version March 2015.

Prior and concomitant medications will be summarized by the preferred term and treatment group for the safety population. Concomitant medications that are taken during the double-blind treatment period will be included in the summary table. All reported medications (including those initiated after the last dose of double-blind study medication) will be included in the listing. For the summary tables, if a subject has taken a prior or concomitant medication more than once, the subject will be counted only once for the medication.

3.6. Treatment Adherence Rate and Extent of Exposure

3.6.1. Treatment Adherence Rate

Treatment adherence to the daily dosing schedule of samidorphan and placebo during the double-blind period will be summarized by treatment group for the safety population. Treatment adherence will be calculated as follows:

$$100 \times \frac{\text{Total tablets dispensed} - \text{total tablets returned} - \text{total tablets lost}}{\text{Total tablets scheduled to be taken}}$$

3.6.2. Extent of Exposure

Exposure (days) on study drug is defined as the number of days from the date of the first dose of study drug taken to the date of the last dose taken, inclusive, for the relevant period. Exposure to

study drug will be summarized for each population; overall for the open-label periods and by treatment group for the double-blind period.

The olanzapine dose level at the start of the double-blind treatment period (V8) will be summarized by treatment group and overall.

3.7. Efficacy Analyses

3.7.1. General Considerations

All statistical tests will be 2-sided hypothesis tests performed at the 5% significance level. All confidence intervals will be 2-sided 95% confidence intervals, unless specified otherwise.

3.7.2. Primary Efficacy Endpoint

The primary efficacy endpoint is defined as the time from randomization to the first EEDS.

An EEDS is defined as any of the following occurring during the double-blind period and is related to worsening of disease symptoms, as confirmed by the IAC ([protocol section 11.1¹](#)):

1. Subject requires hospitalization due to worsening of disease symptoms including a psychiatric hospitalization or a hospitalization due to or for acute treatment of alcohol intoxication or withdrawal
2. Subject has a $\geq 25\%$ or ≥ 15 -point increase from randomization in PANSS total score that is confirmed at a second, ad hoc visit shortly after the first assessment
3. Subject has a PANSS item score of P1, P2, P3, P6, P7, or G8 that meets one of the following criteria:
 - For subjects with a score ≤ 3 at randomization, a score ≥ 5 that is confirmed at a second, ad hoc visit shortly after the first assessment
 - For subjects with a score of 4 at randomization, a score ≥ 6 that is confirmed at a second, ad hoc visit shortly after the first assessment
4. Subject commits deliberate self-injury, engages in aggressive behavior, or displays signs of suicidal or homicidal ideation that is clinically significant as judged by the PI
5. Subject requires initiation of rescue medication, including an increase in prescribed olanzapine dose level, due to worsening of disease symptoms
 - For this study, the increase in olanzapine dose must be above the randomization dose level even if the dose level is previously decreased at some point after randomization.
6. Subject requires an emergency room visit due to worsening of disease symptoms
7. Subject withdraws or PI discontinues the subject from the study for one of the following reasons:
 - a. Lack of efficacy
 - b. Lost to follow-up
 - c. Withdrawal by subject

8. Subject is involved in an incident leading to arrest or incarceration during the study period that is related to the subject's underlying disease

For criterion requiring a consecutive assessment, the second assessment should be scheduled within 3-7 days of the first occurrence and conducted as per [Section 8.5 of the protocol](#)¹. All EEDS cases will be reviewed by the IAC in a blinded manner. Only events confirmed by the IAC will be used for efficacy analyses. Further details on the functioning of the IAC are included in the [IAC charter](#)².

Subjects who completed or discontinued the double-blind period without an EEDS will be censored at the last EEDS assessment date. For all other subjects with EEDS, the date of first EEDS will be counted as event date.

3.7.2.1. Primary Analysis of the Primary Efficacy Endpoint

For the primary analysis of time to the first EEDS, comparison of the 2 treatment groups will be carried out using a log rank test. The Cox proportional hazards model will be used to obtain an estimate of the hazard ratio for the ALKS 3831 group to the olanzapine group adjusting for the baseline PANSS total score and drinking status. A 95% confidence interval will be computed for the hazard ratio.

Kaplan-Meier estimates of EEDS rate will be generated and the Kaplan-Meier plot of time to first EEDS will be presented by the treatment group.

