10. In the opinion of the PI or designee, the subject is not a danger to himself/herself or others and has no elevated suicidal ideation or behavior at the time of screening and the subject answers “No” to items #4 and #5 of the Columbia Suicide Severity Scale (C-SSRS) for ideation and behavior in the 30 days prior to screening and Visit 2.
- Although a recent exacerbation of symptoms is needed for inclusion in the study and suicidal behavior may qualify as an exacerbation, a subject who still represents a danger to him/herself at the time of screening is not eligible for this study.
11. Has experienced at least 10 drinking days (a day in which the subject had at least 1 standard alcoholic drink) within the 30 days prior to screening (as assessed by Timeline Follow-Back [TLFB] self-report using the TLFB definition for a standard drink)
- At least 2 of these drinking days must be heavy drinking days, defined as 4 drinks in 1 day for women or 5 drinks in 1 day for men.
12. In accordance with the locally approved informed consent form (ICF), subjects at some sites may be required to have an informant or caregiver who meets some or all of the following criteria:
- a. Informant or caregiver will be in contact with the subject several times per week.
 - b. If necessary, the informant or caregiver will accompany the subject to visits.
 - c. Informant or caregiver will help ensure maximum subject adherence to study procedures.
 - d. The informant or caregiver must be willing and able to provide informed consent by signing the caregiver ICF.
- In Bulgaria, subjects are required to have an informant or caregiver who meets criteria 12a, 12b, 12c and 12d.
13. Agrees to use an acceptable method of contraception for the duration of the study unless surgically sterile or postmenopausal

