9.3. Randomization to Treatment

At Visit 8, subjects will be randomized to receive one of the following regimens in a 1:1 ratio:

- Olanzapine + Samidorphan (10 mg)
- Olanzapine + Placebo

Randomization will be performed centrally through an Interactive Web Response System (IWRS). A unique randomization number will be assigned by an IWRS once eligibility has been determined. Once a randomization number has been assigned, that number must not be used again if, for example, a subject is withdrawn from the study. Codes will be prepared by a third-party biostatistician who is not otherwise involved in this study.

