2. SAMPLE SIZE CONSIDERATION

The sample size calculation is based on the detection of hazard ratio for the first event of exacerbation of disease symptoms (EEDS) during the double-blind treatment period.

Based on the previous clinical studies with olanzapine and clinical judgment, the 9-month cumulative proportion of subjects experiencing an event of exacerbation of disease symptoms (EEDS) will be 15% and 30% for the ALKS 3831 group and olanzapine plus placebo group, respectively. Assuming an exponential distribution of survival time, and a 2-sided test at $\alpha=0.05$, a total of 70 EEDS will be required for approximately 90% power to detect a hazard ratio of 0.45 between ALKS 3831 and olanzapine plus placebo with a randomization allocation ratio of 1:1 (ALKS 3831:olanzapine plus placebo). Approximately 270 subjects (135 subjects per treatment group) will need to be randomized at Visit 8 to observe 70 total EEDS.

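### The primary log-rank test and Cox model leave out region in a multinational trial; stratifying by US vs. Non-US costs little and gives a modest gain if region is prognostic

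*SAP*

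**What the plan says.** **Primary analysis (SAP 3.7.2.1).** Time to first EEDS is compared by a log-rank test, with no stratification factor named. A Cox model then gives the "hazard ratio for the ALKS 3831 group to the olanzapine group adjusting for the baseline PANSS total score and drinking status". Region is in neither. Protocol 14.3.1 also plans an unstratified log-rank test, and says only that the Cox model will adjust for various covariates.

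**Randomization (Protocol 9.3).** "At Visit 8, subjects will be randomized to receive one of the following regimens in a 1:1 ratio", centrally through an IWRS. No stratification factor is described.

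**Region elsewhere.** The Protocol synopsis calls the study multinational. SAP 3.4 lists region among the baseline characteristics. SAP 3.7.2.4 makes US vs. Non-US a subgroup for the primary endpoint, analysed in a Cox model with treatment, subgroup and their interaction. Neither sensitivity analysis in SAP 3.7.2.2 adds region.

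**Design figures (SAP 2).** The 9-month EEDS proportions "will be 15% and 30% for the ALKS 3831 group and olanzapine plus placebo group, respectively", and "a total of 70 EEDS will be required for approximately 90% power to detect a hazard ratio of 0.45". "Approximately 270 subjects (135 subjects per treatment group) will need to be randomized at Visit 8 to observe 70 total EEDS".

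**The concern.** Several EEDS criteria reflect local services as well as the illness: hospitalization, emergency room visit, arrest or incarceration, loss to follow-up and withdrawal. Blinded adjudication decides whether a reported event is related to the disease; it cannot equalize how readily care is sought or given. The protocol also lets conduct differ by country: "In Bulgaria, subjects are required to have an informant or caregiver who meets criteria 12a, 12b, 12c and 12d". Under Protocol 7.7, a Bulgarian subject whose caregiver cannot be replaced must leave the study, whereas most subjects elsewhere may continue.

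If background EEDS rates do differ by region, two things follow. A log-rank test that pools regions is less efficient than one that compares arms within region. And a chance difference between arms in regional mix moves the unstratified estimate. The study stops by calendar, about 9 months after the last randomization (Protocol 8), so lost efficiency cannot be recovered by waiting for more events.

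**Working it through.** **1. The plan's own figure.** Exponential times give an implied HR = ln(0.85)/ln(0.70) = 0.456. Schoenfeld's formula for 1:1 allocation and a two-sided 5% test is d = 4(1.960 + 1.282)²/(ln HR)². It gives 66 events at HR 0.45 and 69 at 0.456. With 70 events, power = Φ(√70 × |ln 0.45|/2 − 1.960) = Φ(1.38) = 91.6%, or 90.8% at 0.456. The stated 70 events for about 90% power is reproduced.

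**2. Power with and without stratification.** From the documents: 135 per arm, 30% control risk at 9 months, follow-up of 9–15 months. Assumed, because the documents give no figures: the US share p, the US:non-US hazard ratio k, and the dropout rate. The base hazard λ solves p(1 − e^(−9kλ)) + (1 − p)(1 − e^(−9λ)) = 0.30, so the overall control risk stays at the plan's value. The unstratified statistic is U/√V over all subjects; the stratified one is (U_US + U_nonUS)/√(V_US + V_nonUS).

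Analysis at the 70th event, HR 0.45, 20,000 simulated trials per row (Monte Carlo error about 0.2 points):

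| k | p = 50%: unstratified / stratified | p = 30%: unstratified / stratified |
|---|---|---|
| 1 | 91.9 / 91.7% | 91.3 / 91.1% |
| 1.5 | 91.4 / 91.5% | 91.7 / 91.9% |
| 2 | 91.1 / 91.9% | 90.8 / 91.6% |
| 3 | 90.0 / 91.9% | 89.4 / 91.5% |

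Follow-up of 9–15 months is closer to the plan. With HR 0.456, p = 50% and 20% non-EEDS dropout by 9 months (6,000 trials per setting; k = 2 was run twice):

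| k | unstratified / stratified |
|---|---|
| 1.25 | 88.8 / 88.8% |
| 1.5 | 88.6 / 88.7% |
| 2 | 87.5 / 88.4% and 87.7 / 88.8% |
| 3 | 85.7 / 88.1% |

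Without dropout, the gain at k = 3 is 2–3 points at HR 0.45. It is about 4 points at a weaker assumed HR of 0.60. If k = 1, stratifying costs 0.2 points at 70 events and about 0.3 points in the setting with dropout.

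**3. Type I error.** At HR = 1 and 70 events, both tests reject in 5.0–5.5% of trials across all values of k and p above.

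**4. Chance imbalance.** The SD of the between-arm difference in US share is √(2p(1 − p)/135): √(0.50/135) = 6.1 points at p = 50% and √(0.42/135) = 5.6 points at p = 30%. A 10-point difference is therefore 1.6 to 1.8 SD.

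Its effect can be checked by hand. The average starting hazard in an arm is proportional to 1 + p(k − 1), so a 10-point difference in p multiplies the HR by roughly:

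| k | p = 55% vs 45% | p = 35% vs 25% | simulated |
|---|---|---|---|
| 1.5 | 1.275/1.225 = 1.04 | 1.175/1.125 = 1.04 | about 1.04 |
| 2 | 1.55/1.45 = 1.07 | 1.35/1.25 = 1.08 | 1.07–1.08 |
| 3 | 2.10/1.90 = 1.11 | 1.70/1.50 = 1.13 | 1.11–1.14 |

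The shift goes either way, depending on which arm has more subjects from the higher-risk region. For scale, the SE of log HR with 70 events is about 2/√70 = 0.24. A factor of 1.08 is ln(1.08)/0.24 = 0.32 SE, and a factor of 1.14 is 0.55 SE.

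**The case against.** The strongest reply is that the harm is assumed. Neither document gives EEDS rates by region, the regional split, or any statement that region is prognostic. Up to a ratio of 1.5 the gain is essentially nil. That stands, and it limits the point to a conditional one.

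A reader might infer that power is certainly lost, or that regional imbalance biases the primary result. The documents do not support either. Both effects need region to be prognostic. The unstratified test keeps its 5% level, and chance imbalance is noise already covered by that error rate. The slightly weaker unstratified HR (about 0.465 against 0.458 at ratio 2) is not an error either: hazard ratios averaged over regions and within regions are different quantities. A reader might also take randomization to be unstratified as a fact; Protocol 9.3 is only silent.

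The country argument has limits too. Caregivers may be required at some sites outside Bulgaria and should be identified whenever possible (Protocol 7.1, 7.6). US vs. Non-US pools Bulgaria with every other non-US country, so it would not isolate that rule. Confirmed PANSS changes, with rater review, depend less on local services. SAP 3.7.2.2 already censors events that meet only the loss-to-follow-up or withdrawal criteria.

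It can be said that SAP 3.7.2.4 handles region already. It does so only in part: a model with a treatment-by-region interaction gives region-specific hazard ratios, not a region-adjusted overall effect, and it leaves the primary p-value unchanged. Tabulating region by arm would show an imbalance but not correct for it.

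Finally, stratifying does not always help in a given trial. At an assumed HR of 0.63 and ratio 2, 4.5% of simulated trials gained significance and 3.2% lost it. This is why the choice must be made before unblinding.

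**Conclusion.** The point holds as a modest improvement in efficiency and robustness. The planned primary test is valid, and the event calculation is reproduced. What is missing is adjustment for a baseline factor that the SAP already collects and defines, for an endpoint partly driven by local services.

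The size depends on an unknown US:non-US hazard ratio. At the design effect, stratifying gains about 0 points of power at a ratio of 1.5, about 1 at 2 and 2–3 at 3. A 10-point imbalance in US share moves the HR by a factor of about 1.07–1.08 at ratio 2, or 1.11–1.14 at ratio 3. If region is not prognostic, the loss is about 0.2–0.3 points. These figures rest on an assumed US share of 30% or 50%, exponential times and, where stated, 20% dropout. The case for acting is that the cost is small and known while the possible gain is larger.

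**What to change.** Before unblinding, amend SAP 3.7.2.1 to:

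- stratify the log-rank test and the Cox model by US vs. Non-US, as defined in SAP 3.7.2.4;
- keep baseline PANSS total score and drinking status as Cox covariates;
- report the unstratified log-rank test alongside.

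If the sponsor keeps the unstratified log-rank test as primary, add region to the Cox hazard-ratio model and pre-specify the region-stratified log-rank test in SAP 3.7.2.2 as a sensitivity analysis.

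Also state whether the IWRS used any stratification factor. Because Protocol 14.3.1 names a log-rank test without strata, record a change of the primary test in SAP Section 5. No new data are needed. The cost is SAP wording and, if region is not prognostic, about 0.2–0.3 points of power.

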3.7.2.2. Sensitivity Analysis of the Primary Efficacy Endpoint

As sensitivity analysis, if the first adjudicated EEDS only satisfies the discontinuation criterion, (either satisfies 7b or 7c criteria in EEDS definition, or if IAC doesn't specify a criterion), it will be censored at the last EEDS assessment date. Analysis will be the same as the primary analysis of EEDS.

Additional sensitivity analysis will be performed to assess the potential impact of informative censoring. 10%, 20% and 30% of subjects who discontinued from the study without any EEDS will be randomly assigned as having EEDS one day after the discontinuation. Twenty imputations will be carried out. The generated datasets will be analyzed similarly as the primary analysis using the cox proportional hazard model. Rubin's rule will be used to combine the treatment effect estimates and standard errors across imputations.

3.7.2.3. Additional Analysis of the Primary Efficacy Endpoint

Exploratory analysis will be performed to analyze the relationship of the primary endpoint to the drinking profiles during the double-blind treatment period. Percent of heavy drinking days during the double-blind treatment period will be subset into quantiles and used as the factor in the Cox proportional hazards model. The model will also adjust for the baseline PANSS total score. Kaplan-Meier estimates of EEDS rate will be generated.

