5. INTRODUCTION

ALKS 3831 is a combination of olanzapine and samidorphan (previously referred to as ALKS 33 or RDC-0313) being developed for the treatment of schizophrenia. Olanzapine has been available in the United States (US) and Europe since 1996 and was originally approved for the treatment of schizophrenia [EMEA 2013; Lilly USA 2013]. Olanzapine is regarded as one of the most effective antipsychotics with well-recognized efficacy and other advantages such as decreased incidence of extrapyramidal symptoms [Lieberman, 2005]. However, its efficacy and safety have not been fully evaluated in patients with schizophrenia and alcohol use disorder (AUD). Furthermore, the use of olanzapine in treatment has been limited by adverse events (AEs) related to weight gain and unintended metabolic effects.

Samidorphan is a μ -opioid receptor antagonist being developed on its own for treatment of reward disorders and in combination with olanzapine (ALKS 3831) for treatment of schizophrenia. In ALKS 3831, samidorphan has a range of potential benefits for patients with schizophrenia, such as reducing alcohol consumption and attenuating weight gain. Both of these benefits have the potential to improve long-term outcomes, such as reducing schizophrenia symptom severity and decreasing the frequency of events of exacerbation of disease symptoms (EEDS). ALK3831-401 is designed to assess efficacy of ALKS 3831 on time to EEDS after randomization to ALKS 3831 or olanzapine plus placebo following a recent exacerbation (within 6 months prior to screening) in schizophrenia with AUD. A separate study (ALK3831-302) is ongoing to assess other potential benefits of ALKS 3831 in schizophrenia.

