If no withdrawal criteria have been met, subjects experiencing an EEDS (except event #7) may continue in the study at the discretion of the PI.

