3.7.3.1. Rate and Number of EEDS

3.7.3.1.1. Primary Analysis on the Rate and Number of EEDS

Considering EEDS as recurrent events, an Andersen-Gill mean/rate intensity model will be employed to analyze the time-to-recurrent EEDS. This model will allow for an arbitrary dependence structure of the recurrent events within the same subject by using a robust “sandwich” estimate of the covariance matrix. The model will also adjust for the baseline PANSS total score and drinking status. The estimated hazard ratio (and 95% confidence interval) of the ALKS 3831 group to the olanzapine group will be calculated under the Anderson-Gill mean/rate intensity model.

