3.7.4.6. Complete Response Profile of Drinking during the Double-blind Treatment Period

Complete response profile of drinking during the double-blind treatment period will be analyzed by the following endpoints:

- Proportion of subjects with at least 1 level decrease in World Health Organization (WHO) drinking risk level from baseline by visit
- Proportion of subjects with at least 2 levels decrease in World Health Organization (WHO) drinking risk level from baseline by visit
- Proportion of subjects abstinent from heavy drinking days from randomization through week 24 of the double-blind treatment period (study week 27)
- Proportion of subjects abstinent from heavy drinking days by visit
- Proportion of subjects abstinent from drinking days by visit
- Number and rate of heavy drinking days
- Number and rate of drinking days
- Percent of heavy drinking days cumulatively from baseline through weeks 12, 24, 36, 48 and 60 of the double-blind treatment period
- Percent of drinking days cumulatively from baseline through weeks 12, 24, 36, 48 and 60 of the double-blind treatment period
- Percent of heavy drinking days by visit during the double-blind treatment period
- Percent of drinking days by visit during the double-blind treatment period
- Number of drinks per day by visit during the double-blind treatment period
- Number of drinks per drinking day by visit during the double-blind treatment period

In general for the TLFB assessment, by-visit result is defined as the drinking assessments between previous and current visits. It will be 2 weeks of drinking assessments for Visit 9 Week 5 and Visit 10 Week 7, and monthly thereafter.

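### The exploratory Cox model of drinking and EEDS uses whole-period heavy drinking as a fixed factor with no treatment term, so the association can be created, masked or inflated

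*SAP*

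**What the plan says.** SAP 3.7.2.3, labelled exploratory, relates the primary endpoint to drinking: "Percent of heavy drinking days during the double-blind treatment period will be subset into quantiles and used as the factor in the Cox" model. Baseline PANSS total is the only other term named. The section gives no lag, landmark, time-dependent covariate or cut-off at the event, and it does not name treatment group or baseline drinking status. It also plans Kaplan-Meier estimates.

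Other sections bear on this:

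- Protocol 11.1: "subjects experiencing an EEDS (except event #7) may continue in the study at the discretion of the PI". TLFB stays on the visit schedule (Protocol Tables 2 and 3), and SAP 3.7.3.1.1 expects repeat events: "Considering EEDS as recurrent events, an Andersen-Gill mean/rate intensity model will be employed to analyze the time-to-recurrent EEDS".
- SAP 3.7.2, criterion 7, counts some departures as events: "Subject withdraws or PI discontinues the subject from the study for one of the following reasons", namely lack of efficacy, loss to follow-up and withdrawal by the subject.
- Protocol 5 expects that "samidorphan has a range of potential benefits for patients with schizophrenia, such as reducing alcohol consumption and attenuating weight gain", and adds: "Both of these benefits have the potential to improve long-term outcomes, such as reducing schizophrenia symptom severity and decreasing the frequency of events".
- SAP 3.7.2.1 adjusts the treatment hazard ratio for baseline PANSS and drinking status, and SAP 3.7.2.4 puts treatment in the subgroup models.
- SAP 3.7.4.6.3 removes some drinking records after stopping study drug, hospitalization or incarceration, but only in sensitivity analyses of the cumulative drinking endpoints.

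**The concern.** At each event time a Cox model compares the subject who has the event with those still at risk, so the covariate should be known at that time. Here it is an average over days that may lie after the event. This raises two timing problems and one omission.

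1. If drinking changes after an EEDS and the subject stays, the factor partly records a consequence of the event.
2. If the event is a criterion 7 departure, the factor covers only the time up to it. A percentage is already scaled for length, so this matters only if drinking trends over time: early leavers are then averaged over a different stretch of the trend from those who stay.
3. If treatment lowers drinking and also lowers EEDS by some other route (Protocol 5 names weight gain), leaving treatment out credits part of that other effect to drinking.

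This is the analysis that would link the proposed mechanism, less drinking, to the primary endpoint. As specified, a reader could not tell whether the drinking came before the EEDS or after it.

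**Working it through.** **The plan's own figure.** With 15% and 30% at 9 months and exponential times, HR = ln(0.85)/ln(0.70) = 0.4556. Schoenfeld events = 4(1.960 + 1.2816)²/(ln 0.4556)² = 42.03/0.618 = 68.03, so 69; at HR 0.45 the result is 66. Power with 70 events is 90.8% at 0.4556. The stated 70 reproduces. Expected events are 135 × 0.15 + 135 × 0.30 = 60.75 at 9 months, and about 77 with follow-up uniform over 9 to 15 months and no dropout. SAP 3.7.2.3 itself states no figure.

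**How the factor moves.** For illustration, assume 27% heavy drinking days, an EEDS at week 12, observation to week 48, and odds that fall threefold after the event. Odds before are 0.27/0.73 = 0.370; after, 0.123, which is 11.0%. The whole-period value is 0.25 × 27 + 0.75 × 11.0 = 15.0%. A subject at 27% before the event is analysed as 15%.

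**Simulation 1** (200 trials per scenario, so a Monte Carlo SE of about 1.5 points at 5%). From the plan: 270 subjects 1:1, 9 to 15 months. Assumed: mean logit of daily heavy drinking -1.4, SD 1.2; drift ±0.4 logit per 13 weeks; post-EEDS change +1.0 or -1.5 logit; 0%, 50% or 100% staying after an EEDS; treatment effect on drinking -1.0 logit unless stated, with a separate EEDS HR of 0.456. PANSS was not simulated, and quantiles were read as quartiles. Entries are the top-versus-bottom-quartile HR (share of trials with p<0.05).

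| Scenario | SAP factor, no treatment term | Lagged cumulative percent plus treatment |
|---|---|---|
| No link, no drift or post-event change | 0.97-1.02 (4%) | 0.99-1.02 (4-7%) |
| No link, drinking falls over time, half stay | 1.32 (15%) | 0.97 (4%) |
| No link, falls over time, none stay | 1.91 (52%) | 1.04 (3%) |
| No link, rises over time, none stay | 0.47 (66%) | 1.06 (7%) |
| No link, rises after EEDS, half stay | 1.65 (28%) | 1.00 (4%) |
| No link, rises after EEDS, all stay | 2.78 (92%) | 0.97 (6%) |
| No link, treatment lowers both separately | 1.40 (19%) | 0.95 (4%) |
| Same, drinking effect -0.5 logit | 1.16 (7%) | 0.99 (4%) |
| True link, undistorted | 2.34 (77%) | 2.38 (69%) |
| True link, falls after EEDS, half stay | 1.24 (13%) | 2.32 (68%) |
| True link, falls after EEDS, all stay | 0.70 (17%) | 2.38 (73%) |
| True link, rises after EEDS, half stay | 3.87 (99%) | 2.44 (73%) |
| True link, falls over time, none stay | 4.55 (99%) | 2.40 (70%) |
| True link plus separate treatment effect | 3.57 (97%) | 2.50 (73%) |

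The timing and treatment faults are separate. Adding treatment alone leaves 1.91 at 1.91; lagging alone gives 1.42 where the treatment fault gave 1.40.

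**Simulation 2** (1,000 replicates in each of 53 scenarios, SE about 0.7 points at 5%). Assumed: 27% heavy drinking days, between-subject SD 1.2 to 1.8 on the logit scale, 40% of events withdrawals, follow-up 36 to 60 weeks.

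- No link, lasting threefold odds change after all, half, a quarter or a tenth of non-withdrawal events: the SAP model rejects 15-38%, 7-12%, 3-6% and 4-5%. Abstinence after every such event gives 4% (14 days), 7% (30 days) and 18% (90 days).
- No link, treatment lowers heavy-drinking log-odds by 0.5 to 1.0: HR 1.12-1.44 (5-10% rejection) without a treatment term, 0.97-0.99 (5-6%) with one.
- True link, undistorted HR 1.92: 1.02, 1.36 and 1.61 if odds fall threefold after all, half or a quarter of non-withdrawal events; 3.61, 2.63 and 2.24 if they rise.
- No link, log-odds falling by 1 to 2 over the first 24 weeks: the SAP model rejects 6-15%. Cutting records at the event and adding treatment rejects 13-71%. A time-dependent percent with treatment and PANSS rejects 3.8-5.7%.
- Over all 44 null scenarios that time-dependent model rejects 3.4-6.9%. With the true link it rejects 51-59%, whatever happens after the event. Adding baseline drinking lowers this to 8-11% when drinking is stable within subjects.

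**The case against.** The stakes are low. The analysis is exploratory, Protocol 14.3.1 makes it optional and open to other methods, and it informs no primary or secondary endpoint. This stands, and it sets the severity.

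The large distortions need strong inputs. In simulation 2, when only a quarter of non-withdrawal events change drinking, null rejection is 3-6%. That too stands, although a true HR of 1.92 is still reduced to 1.61 in that case.

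Protocol 5 presents less drinking as a route to fewer EEDS. A reader might infer that any effect of treatment on drinking contaminates the estimate. The documents do not support that: if treatment prevents EEDS by reducing drinking, that is a drinking effect. Confounding needs another route, and even then the null rejection in simulation 2 is only 5-10%.

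Dataset and programming specifications are separate documents (SAP 6 and 8), so a cut-off rule may exist there. The SAP states none, and a plain cut at the event would not be a safe rule.

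The loss of power could be offered as a reason to keep baseline drinking out. It is a weak one, since SAP 3.7.2.1 adjusts for it. The better approach is to report both models.

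**Conclusion.** The point holds as a risk and is minor. Followed as written, SAP 3.7.2.3 can mix post-event drinking and outcome-dependent windows into the exposure, and it omits a plausible common cause. The timing faults are the larger part.

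The size is unknown. The documents give no drinking distribution, trend, post-EEDS change, share staying or share of events that are withdrawals, so every simulated figure rests on assumption. A reader might infer that the reported association will be wrong, or wrong by one of the amounts above; the documents support only that it can be.

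The opposite inference, that all is well if few events change drinking and treatment leaves drinking alone, also fails. Drift alone gave 6-15% null rejection in simulation 2, and 52% or 66% in simulation 1 when every EEDS ended follow-up. The model is undistorted only if drinking neither changes after an EEDS nor drifts over time, and treatment does not act on both drinking and, separately, EEDS.

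The primary log-rank test, alpha and sample size are unaffected.

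**What to change.** Replace the whole-period factor with a time-dependent percent of heavy drinking days. SAP 3.7.4.6 already supplies the unit: "by-visit result is defined as the drinking assessments between previous and current visits". Use the interval value, or the cumulative value, up to the last TLFB visit before each risk time, and the baseline value before the first post-randomization TLFB. Include treatment group and baseline PANSS total.

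Report the model with and without baseline drinking status, noting that adjustment changes the question when drinking is stable within subjects. For any Kaplan-Meier display by drinking group, use a pre-specified landmark. Do not simply truncate records at the event.

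State three limitations: worsening symptoms may change drinking before an EEDS; criterion 1 includes "a hospitalization due to or for acute treatment of alcohol intoxication or withdrawal", so the endpoint partly contains alcohol events; and TLFB values may be stale before loss to follow-up, since recall is capped at 30 days (Protocol 8.3.12) and that status needs at least a month without contact (Protocol 7.4).

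Cost: a few SAP sentences and some counting-process programming, with no new data. The result describes recent or cumulative drinking rather than the whole-period profile, and a landmark display omits earlier events.
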